7.2 Trial Procedure and Treatment

7.2.1 Outline of Treatment Plan

Patients will receive standard or investigational treatment according to the table below.

Standard treatment:

Treatment	Dose (units)	Route	Treatment Period
ATGAM (Pfizer)	40 mg/kg/day	i.v., 12-18 h infusion	Day 1, 2, 3 and 4
Cyclosporine A	5 mg/kg/day	Orally	Day 1-365 (adjusted on blood levels)

Investigational treatment:

Treatment	Dose (units)	Route	Treatment Period
ATGAM (Pfizer)	40 mg/kg/day	i.v., 12-18 h infusion	Day 1, 2, 3 and 4
Cyclosporine A	5 mg/kg/day	Orally	Day 1-365 (adjusted on blood levels)
Eltrombopag	150 mg every 24 h (50 mg tablets x3)	Orally	Day 14-90 (or 14-180)

7.2.2 Treatment Assignment

Administration of randomisation is separated from the clinical investigators. Randomisation will be stratified according to center (each center of expected size ≥ 20 being a single stratum and all smaller centers lumped together), age (≥ 15 and < 40 year old vs. ≥ 40 year old) and disease severity (severe aplastic anemia vs. very severe anemia). The ratio of patients included in each arm for standard treatment versus investigational treatment is to be 1 : 1.

7.2.3 Duration of Patient Participation

Patients will be included in the trial following informed consent. Following registration patient will start hATG within 7 days. Patients have to be randomised at, or the day before, start of hATG treatment.

Patients will remain on the trial for 2 years (for treatment and subsequent follow up); the duration of the treatment with the IMP will be initially 3 or 6 months (depending on hematological response). However, given that re-introduction of the IMP is allowed for 6 additional months, the treatment duration may be extended up to 18 months from enrolment. Per protocol, eltrombopag (the investigational agents) will be administered for a maximum period of 12 months: maximum 6 months at enrolment, plus additional maximum 6 months in

case of early relapse. As long-term effects of investigational treatments are an objective of the study, the follow-up of patients will cover a minimum of 24 months from initial randomisation. The long term follow up of the patients will be conducted outside of the protocol and will be extended up to 10 years from treatment, through the EBMT official database (updated EBMT Registry Database).

7.2.4 Evaluation and Visit Schedule

Visit schedule (see also flowchart in the appendix 2)

7.2.4.1 Baseline (Visit 0)

Refer to the table/flow chart in the appendix 2 for the list of baseline tests.

All patients must provide fully informed written consent before any procedures are done. All baseline tests must be completed within 30 days before registration.

All the tests except for the cataract check up are part of routine clinical care of AA patients, therefore results from tests that are performed no more than 30 days prior to registration can be used to assess the patients eligibility.

The following tests will be performed at the baseline visit in all patients.

- Medical history, including all concomitant diseases
- Review diagnosis of aplastic anemia, including subclassification
- Physical examination, including review of systems
- Review of signs and symptoms of AA (including infections)
- Hematology (WBC with complete differential, platelets, reticulocytes, hemoglobin) within 2 week prior enrollment
- Past history of packed red blood cells (PRBC) and platelet transfusions
- Bone marrow aspirate, including:
 - Cytology study
 - Flow cytometry study
 - Karyotype study (centralized)
 - Molecular studies (for research purpose only: sample to be centralized)
- Bone marrow trephine biopsy
- Peripheral blood immunophenotyping looking for:
 - Expression of glycosylphosphatidylinositol anchored proteins for screening of a PNH clone on erythrocytes, neutrophils, monocytes and lymphocytes
 - Analysis of lymphocyte subsets (CD3+, CD4+, CD8+, CD56+, CD19+)
 - Additional immunologic studies including study of activation and effector markers (Th1/Tc1, Th2/Tc2, Th17, Tregs, T naïve, T central memory, T effector memory, T effector) (for research purpose only: sample to be centralized)
- Chromosomal breakage test for all subjects <20 years of age and >20 years of age suspicious for constitutional aplastic anemia (i.e. Fanconi's Anemia or Dyskeratosis Congenita)
- Complete screening for hepatic, cardiac and renal function (including serum creatinine, BUN, bilirubin, LDH, AST, ALT, total proteins, albumin, Na, K)
- Telomere length (centralized)
- Quality of life questionnaire (EORTC QLQ-C30)³

³ The QoL questionnaire will be administered to the patient before the visit, and, according to standard guidelines, it will be filled independently from the treating physician to avoid biased information.

- Review all records to be included in CRF
 - Blood transfusions
 - Clinical infections, including type, duration, treatment and outcome
 - Adverse effects
 - Signs and symptoms of serum-sickness
- Concomitant medications
- Pregnancy test (HCG) in women of child bearing potential
- Cataract check up

More information about the additional tests performed at the central lab are provided in the Lab manual (Appendix 8).

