7.1 Patient Registration/ Randomisation

To register a patient in the trial the site must complete the RACE registration form and fax this to the EBMT CTO. The registration form must be signed by the PI or Co-Investigator listed on the staff delegation log.

On receipt of the patient registration form the patient data will be entered in the Clinical Trials Management System (CTMS) and the patient will be assigned a unique patient number. The EBMT CTO will send a registration confirmation to the site.

A patient will be considered enrolled in the study when registration of the patient is confirmed by the EBMT Clinical Trials Office.

Randomisation will take place on the day or day before hATG is started. The time between registration and randomisation should be no longer than 7 days.

To randomise a patient the site must complete the RACE randomisation form and fax this to the EBMT CTO. The randomisation form must be signed by the PI or Co-Investigator listed on the staff delegation log.

The patient data will be entered in the CTMS and the patient will be randomised to either the standard or the investigational arm. The EBMT CTO will send the randomisation result to the site.

Randomisation ratio will be 1:1. Randomisation will follow a stratified variable length block design. Stratification will be done according to patient's age and disease severity to ensure homogeneity between treatment arms, according to the following subgroups:

Disease severity:

- Severe aplastic anemia (SAA)
- Very severe aplastic anemia (VSAA: SAA plus ANC <200/ μ L)

Age:

- ≥ 15 and <40 year old
- ≥ 40 year old

A stratification by centre will be considered as an additional balancing factor for randomisation, based on the center size (i.e. the number of patients expected to be entered into a center in this trial). A center is classified as "large" if the anticipated number of patients to be entered exceeds 20. Otherwise the center is classified as "small". All centers classified as small will be treated as one single stratum; all large centers have their own stratum. Hence randomisation will be balanced within each large center on disease severity and age; and likewise within the pool of all small centers.

Patient registration and randomisation forms will be processed Monday to Friday from 09.00 -17.00 CET.

- Forms received after 17.00 will be processed the next day.
- Forms received over the weekend will be processed the following Monday morning.

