APPENDIX 2 Summary of Evaluation and Visit Schedule

Procedure	Visit 0	Visit 1	Visit 2,3,4,5	Visit 6,7,8	Visit 9	Visit 10,11	Visit 12	Visit 13,14	Visit 15	Visit 16,17	Visit 18	Visit 19	Visit 20	Visit 21	Visit 22
Time	Pre	d0-1	w1,2,3,4	m1.5,2,2.5	m3	m4,5	m6	m7,8	m9	m10,11	m12	m15	m18	M21	m24
Medical history	X														
Diagnosis	X														
Physical examination	X	X	X	X	X	X	X	X	X	X	X	X	X	X	X
Signs and symptoms	X	X	X	X	X	X	X	X	X	X	X	X	X	X	X
Hematology	X	X	X	X	X	X	X	X	X	X	X	X	X	X	X
Transfusion record	X	X	X	X	X	X	X	X	X	X	X	X	X	X	X
Bone Marrow [#]	X*				X [§]		X*				X				X*
Trephine biopsy	X						X				X				X
Immunophenotype	X*						X*				X				X*
DEB test	X [^]														
Biochemistry	X	X	X	X	X	X	X	X	X	X	X	X	X	X	X
Telomeres	X*						X*								X*
QoL	X						X				X				X
Concomitant medications	X	X	X	X	X	X	X	X	X	X	X	X	X	X	X
All record review	X	X	X	X	X	X	X	X	X	X	X	X	X	X	X
HCG	X ^{^^}														
CsA level			X	X	X	X	X	X	X	X	X	X	X	X	X
Treatment Compliance			X	X	X	X	X	X	X	X	X	X	X	X	X
Ophthalmologic function (cataracts)	X				X		X				X	X	X		X
Safety Monitoring	X	X	X	X	X	X	X	X	X	X	X	X	X	X	X

[figure not shown]
*: centralized samples

[§]in the case of CR, at 3 months bone marrow (BM) evaluation is to be performed.

[^]: only in patients <=20y, or with familiar history of AA; ^{^^}: female patients only

[#]additional BM may be performed according to clinical needs and standard practice: clonal evolution implies BM evaluation, by definition.

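### In the visible schedule the only pregnancy test can be 37 days old at the first ATGAM dose and about 50 days old at the first eltrombopag dose; a repeat before randomisation should be added

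*Protocol*

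**What the plan says.** Inclusion criterion 6 (Protocol 6.1) requires a negative pregnancy test and gives no timing. Exclusion criterion 10 (6.2) bars pregnant patients.

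The timing comes from 7.2.4.1. The list of baseline tests contains "Pregnancy test (HCG) in women of child bearing potential" with no window attached, so the general rule governs it: "All baseline tests must be completed within 30 days before registration". The section also accepts existing results: "results from tests that are performed no more than 30 days prior to registration can be used to assess the patients eligibility". One laboratory item is held to a shorter window: "Hematology (WBC with complete differential, platelets, reticulocytes, hemoglobin) within 2 week prior enrollment".

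Appendix 2 marks the HCG row once, at Visit 0, with a footnote limiting it to "female patients only". There is no mark at Visit 1 (day 0-1), at week 2 or at any later visit.

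Three statements link registration to treatment. Section 7.2.3 says: "Following registration patient will start hATG within 7 days". Section 7.1 says: "The time between registration and randomisation should be no longer than 7 days", and also: "Randomisation will take place on the day or day before hATG is started". Eltrombopag begins on day 14 (7.2.1 and 8.1.1). Sections 8.1.1.3 (re-introduction) and 8.11.1 (open-label course for control-arm non-responders) do not mention a pregnancy test. Section 8.11.1 does ask for a marrow karyotype at that point.

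**The concern.** The test that supports inclusion 6 and exclusion 10 is tied to registration, not to randomisation or to a first dose. A pregnancy that begins after the test, or that was too early for it to detect, can go unnoticed until after treatment has started. Both arms receive ATGAM, so the gap is not confined to the investigational arm.

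The footnotes in section 6 give mixed information on the hazard:

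- **Eltrombopag:** not teratogenic in rats and rabbits, with minor fetal effects at maternally toxic doses. Its effect in human pregnancy is described as unknown.
- **ATGAM:** not teratogenic in rats or monkeys up to 20 mg/kg. However, 20 mg/kg/day for 16 days was fetotoxic in monkeys, and 10 mg/kg/day for 16 days was not. The trial gives 40 mg/kg/day for 4 days.
- **Both drugs:** the protocol states that adequate controlled data in pregnant women are lacking.

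What is at stake is avoidable fetal exposure to drugs whose safety in pregnancy is not established.

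**Working it through.** The protocol states no total age for the test, so there is no figure to reproduce. The check adds up the maximum permitted windows.

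**Inputs**

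- HCG to registration: up to 30 days (7.2.4.1).
- Registration to first ATGAM: up to 7 days (7.2.3).
- First ATGAM (day 1) to first eltrombopag (day 14): 14 - 1 = 13 days (7.2.1, 8.1.1).

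**Maximum test age under the current plan**

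- At first ATGAM: 30 + 7 = 37 days.
- At first eltrombopag: 37 + 13 = 50 days.

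**Other readings.** On 7.1 alone, randomisation on day 7 and ATGAM the next day would give 30 + 8 = 38 days; 7.2.3 caps this at 37. If day 14 means 14 elapsed days, the eltrombopag figure rises by one. The full range is 37-38 days at ATGAM and 50-52 days at eltrombopag.

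**Maximum test age with a repeat between registration and randomisation**

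- At first ATGAM: 7 days, a reduction of 37 - 7 = 30.
- At first eltrombopag, with no further test: 7 + 13 = 20 days, a reduction of 50 - 20 = 30.
- At first eltrombopag, with an HCG at the week-2 visit and the dose held for the result: the test is current.

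**Later courses.** Open-label eltrombopag follows non-response at 6 months, so the only scheduled test may then be about 6 months plus up to 37 days old. Re-introduction is allowed within 6 months of stopping, and the first course can run to 6 months. The test could therefore be about 6 + 6 = 12 months plus up to 37 days old.

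**Events, on assumption only.** The documents give neither the number of women of child-bearing potential nor a pregnancy rate. Suppose 40 to 80 such women among the 200 patients and 1 to 10 pregnancies per 100 woman-years. The 30 days removed then correspond to between 40 × 0.01 × 30/365 = 0.03 and 80 × 0.10 × 30/365 = 0.66 pregnancies in the whole trial. This takes every woman to be tested on the first permitted day and started on the last. The upper end also fits poorly with exclusion 15, which requires highly effective contraception.

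**The case against.** The strongest case against is that this is a screening window that could be tighter, not an error. Contraception is required (inclusion 7, exclusion 15 and the footnote on eltrombopag), a woman who suspects pregnancy must tell her physician, pregnancy is a reason to stop treatment (6.3), and pregnancies are reported (10.6). Sites may also retest on their own initiative. All of this lowers the risk and it stands. It does not detect a pregnancy that nobody suspects, and because existing results are accepted, the HCG may even predate consent and the written acceptance of contraception.

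Cost is the second objection. Section 14.6 names the addition of a safety-monitoring test as an example of a substantial amendment needing prior approval. That stands: the assay is cheap, but a stand-alone amendment in a multicentre trial is not.

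Third, simply moving the HCG to after registration would create a conflict. Inclusion 6 must be met for enrolment (6.1), and 7.1 equates enrolment with confirmed registration. This is correct, so the later test has to be a repeat.

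A reader might infer that the protocol breaches its own exclusion 10. It does not: the criterion is clear, and only the age of the evidence for it is loose. A reader might also infer that the present schedule produces randomised patients whom 12.6 then removes from the efficacy analyses. It does not do so through this test, because no HCG is scheduled after randomisation. That problem would arise only if a new test were placed after randomisation, and 12.6 also plans sensitivity analyses that include such cases.

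**Conclusion.** The point holds as a cheap patient-safety improvement. Under the visible schedule, a site in full compliance may give the first ATGAM dose on a negative HCG 37 days old and the first eltrombopag dose on one about 50 days old, with no repeat required. These are outer limits set by the windows, not typical values, and they measure test age, not risk.

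The conclusion rests on Sections 7.1, 7.2 and 8 and Appendix 2. It cannot be read as saying that no repeat test exists anywhere: Section 10 refers to the Appendix 3 flowchart for safety timepoints, and that flowchart and Appendix 7 are not shown. Nor can a number of prevented pregnancies be claimed. The count is likely well below one, on inputs the documents do not supply, so the case rests on the small burden of the remedy.

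**What to change.** - **Baseline:** keep the HCG before registration, so that inclusion 6 is met at enrolment.
- **Before randomisation:** in 7.2.4.1 and the HCG row of Appendix 2, add a repeat for women of child-bearing potential between registration and randomisation. It can use blood already drawn around treatment start, provided it is taken early enough for the result to be known. Record the date and negative result on the RACE randomisation form (7.1). A patient who tests positive is then registered but never randomised.
- **Before first eltrombopag (preferable):** in the investigational arm, add an HCG at the week-2 visit, with the result seen before the first dose.
- **Later courses (preferable):** in 8.1.1.3 and 8.11.1, require a negative HCG on scheduled blood before re-introduced or open-label eltrombopag.

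Cost: a few sentences, a footnote and one form line, a few extra assays, and a result that must be available before randomisation. It may count as a substantial amendment under 14.6 and is best bundled with the next one.

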7.2.4.2 Follow Up visits

See flowchart (appendix 2)

7.2.4.3 Research Samples

In addition to the routine assessments and tests that are done during the baseline and follow up visits (appendix 2), additional procedures and samples will be taken purely for future research purposes (these are unrelated to the RACE study and will not be analysed within the RACE study):

Visit	Procedure	Tests
Baseline	Bone Marrow Aspirate This is a standard procedure but extra sample will be taken for research purposes. In some cases it may be an additional procedure if a clinical sample was taken within 30 days of registration.	Molecular studies
visit 12 & 22	Bone Marrow Aspirate This is a standard procedure but extra sample will be taken for research purposes	Molecular studies
Baseline, visit 12 & 22	Blood Sample This is a standard procedure but extra sample will be taken for research purposes	Immunophenotype & Telomere length

Research samples taken from adults (patients aged ≥ 18 years of age) will be sent to the Central Tissue Bank in the UK. Research samples in minors (< 18 years of age) can be collected and stored at local institutions / tissue banks, providing they follow their local regulations for human tissue collection and storage.

Patients will be asked to sign a second specific consent form in addition to the RACE trial consent form for the collection of the additional samples. Although the samples are being taken from patients in the RACE trial, they are being stored at the King's tissue bank for future research which is separate and not part of the RACE clinical trial. Instead the samples will be part of a future research study that is going to be funded separately.

8. Trial Medication

Eltrombopag is the IMP in this clinical trial, and it will be provided by the company Novartis for the entire duration of this trial. EBMT or Novartis will not provide the drug if the trial has ended (whether prematurely or planned).

ATGAM® (hATG) is a NIMP in this clinical trial and it will be provided by the company Pfizer Inc. (Pfizer) for the entire duration of this trial. When the trial has ended, either planned or prematurely, Pfizer will no longer provide ATGAM to participating institutes.

The other agent, Cyclosporine A is considered standard treatment and the participating sites will provide all the medications according to local practice.

8.1 Trial Medication Description

Described in appendix 3

8.1.1 Eltrombopag

Patients will receive eltrombopag orally at the dose of 150 mg daily, as 50 mg tablets, starting from day 14 (after starting ATGAM).

A 50% dose reduction (50 mg + 100mg eltrombopag on alternating days) is recommended for patients of East Asian heritage (i.e., Japanese, Chinese, Taiwanese and Korean).⁴ Allow at least a 4-hour interval between eltrombopag and other medications (e.g., antacids), calcium-rich foods (e.g., dairy products and calcium fortified juices), or supplements containing polyvalent cations such as iron, calcium, aluminium, magnesium, selenium, and zinc.

No dose adjustment is necessary in patients with renal impairment.⁵ Eltrombopag will not be used in patients with hepatic impairment, which are excluded from this study (see exclusion criteria).⁶

Treatment will be continued at least up to 3 months (75 days of treatment), and then adjusted according to hematological response (see below).

Dose delay or dosing interruptions: eltrombopag dose may be interrupted when clinically indicated at the discretion of the investigator. Interruptions will not be reported as deviations; however when the interruption is consequence to a serious adverse event, the interruption will be included in the report.

⁴A 50% reduced dosing for subjects of fully (both parents) East Asian heritage (i.e., Japanese, Chinese, Taiwanese and Korean) is recommended because plasma eltrombopag AUC(0- τ) concentrations were approximately 80% higher in healthy Japanese subjects compared to non-Japanese healthy subjects who were predominantly Caucasian. Similarly, in patients with ITP, plasma eltrombopag exposure was approximately 70% higher in East Asian subjects as compared to non-East Asian subjects.

⁵ Patients with impaired renal function should use eltrombopag with caution and close monitoring, for example by testing serum creatinine and/or performing urine analysis.

⁶ Eltrombopag should not be used in patients with hepatic impairment (i.e. mild, moderate or severe hepatic impairment (Child-Pugh score ≥ 5) unless the expected benefit outweighs the identified risk of portal venous thrombosis. If the use of eltrombopag is deemed necessary for ITP patients with hepatic impairment the starting dose must be 25 mg once daily.

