	
 • Wash out period of 2 weeks before enrollment. 
 8. CMV viremia, as defined by positive PCR or pp65 test 9. WHO performance status ≥ 3 10. Pregnant or breast feeding patients 11. Patients with hepatic, renal or cardiac failure, or any other life-threatening concurrent disease 12. Patients with HIV infection 13. Patients without social health care assistance 14. Participation in another clinical trial within 1 month before the start of this trial 15. Patients and/or female partners of male patients not using highly effective method of birth control i.e. intrauterine device (IUD), hormonal (oral pill, injection, implants), tubal ligation or partner's vasectomy 16. Subjects with known hypersensitivity to any of the component medications 
The presence of a Paroxysmal Nocturnal Hemoglobinuria clone is not an exclusion criterion. Hepatitis-AA (HAA) syndrome [34] is not an exclusion criterion; similarly, the evidence of HBV or HCV infection is not an exclusion criterion per se, provided that there is no evidence of hepatic failure (see exclusion criterion #11)

Therapy/Intervention	Detailed trial treatment plan included with protocol (appendix 2)
Maximum duration of treatment of a patient	12 months in total during the entire timeframe of the study
Definition of the end of the Trial	Last patient last visit (end of 2 year follow up)
Statistical Plan	
This is a superiority trial aiming to increase the 3 month complete response rate. The sample size is calculated on the hypothesis that the experimental treatment will increase the 3 months response rate up to 21% (by 3 folds, based on the 7% expected in the control group as reported in Scheinberg et al [17]). Under these assumptions, the sample size to reject the null hypothesis is n=96 patients for each treatment arm (two-sided test; alpha-error 0.05; power 0.8). The actual sample size will be increased by 4% to account for possibly not evaluable patients (total number of 200 patients, 100 in each treatment arm).
 
The primary analysis will evaluate complete response rate at 3 months after randomisation; this will be an intention-to-treat analysis. The null hypothesis of no difference in

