6.2 Exclusion Criteria

Patients with one or more of the following criteria cannot be included in the study:

1. Prior immunosuppressive therapy with ATG (horse or rabbit) or any other lymphocyte depleting agent (i.e., alemtuzumab)
2. Eligibility to a sibling allogeneic stem cell transplantation
3. Evidence of a myelodysplastic syndrome, defined by the presence of myelodysplastic features, excess of blasts or karyotypic abnormalities typical of MDS (according to revised WHO 2008 criteria) [30], as well as other primitive marrow disease. Patients with diagnosis of AA with cytogenetic abnormalities which are recurrent in MDS (according to revised WHO 2008 criteria) [30] should be included in this category, and are not eligible for the study; ***patients with del(20q), +8 and -Y are not included in this category, and thus are eligible for this study.*** The list of karyotypic abnormalities which qualifies for the diagnosis of MDS are listed in the Appendix 1.
4. History or clinical suspicion of constitutional aplastic anemia (i.e. Fanconi Anemia with positive DEB/MMC test or Dyskeratosis Congenita)
5. History of malignant tumors with active disease within 5 years from enrollment, and/or previous chemo-radiotherapy
6. Previous history of stem cell transplantation

¹Children in Care (CiC) are not excluded from this study, provided that the agency, organization, institution (or entity of the courts, the government or a government body) will work as legal guardian in signing the informed consent. CiC are defined as children who have been placed under the control or protection of an agency, organisation, institution or entity by the courts, the government or a government body, acting in accordance with powers conferred on them by law or regulation. The definition of CiC can include children cared for by foster parents or living in a care home or institution, provided that the arrangement falls within the definition above. The definition of a CiC does not include a child who is adopted or has an appointed legal guardian.

7. Treatment with cyclosporin A:
 - <4 weeks of cyclosporin A treatment before enrollment.
 - Wash out period of 2 weeks before enrollment.
8. CMV viremia, as defined by positive PCR (≥ 3.5 logarithm) or pp65 test (≥ 5 cells)
9. WHO performance status ≥ 3
10. Pregnant or breast feeding patients^{2,3}
11. Patients with end-stage hepatic, renal or cardiac failure, or any other life-threatening concurrent disease
12. Patients with HIV infection

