Platelet counts above the normal range present a theoretical risk of thrombotic/thromboembolic complications. In eltrombopag clinical trials in ITP thromboembolic events were observed at low and normal platelet counts. Caution should be used when administering eltrombopag to patients with known risk factors for thromboembolism including but not limited to inherited (e.g. Factor V Leiden) or acquired risk factors (e.g. ATIII deficiency, antiphospholipid syndrome), advanced age, patients with prolonged periods of immobilisation, malignancies, contraceptives and hormone replacement therapy, surgery/trauma, obesity and smoking. Platelet counts should be closely monitored and consideration given to reducing the dose or discontinuing eltrombopag treatment if the platelet count exceeds the target levels. The risk-benefit balance should be considered in patients at risk of thromboembolic events (TEEs) of any aetiology; in these patients, prophylaxis of thromboembolic events is allowed at judge of the investigator, with the agents that he will find more appropriate.

The risk of TEEs has been found to be increased in patients with chronic liver disease (CLD) treated with 75 mg eltrombopag once daily for two weeks in preparation for invasive procedures.

The influence of hepatic impairment on the pharmacokinetics of eltrombopag following repeat administration was evaluated using a population pharmacokinetic analysis in 28 healthy adults and 79 patients with chronic liver disease (37 mild hepatic impairment, 40 with moderate hepatic impairment, and 2 with severe hepatic impairment). Based on estimates from the population pharmacokinetic analysis, patients with hepatic impairment had higher plasma eltrombopag AUC(0- τ) values as compared to healthy volunteers, and AUC(0- τ) increased with increasing Child-Pugh score. Compared to healthy volunteers, patients with mild hepatic impairment had approximately 87 % to 110 % higher plasma eltrombopag AUC(0- τ) values and patients with moderate hepatic impairment had approximately 141 % to 240 % higher plasma eltrombopag AUC(0- τ) values.

Eltrombopag should not be used in ITP patients with hepatic impairment (Child-Pugh score ≥ 5) unless the expected benefit outweighs the identified risk of portal venous thrombosis (see section on eltrombopag administration).

Bleeding following discontinuation of eltrombopag

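### Section 8.1.1 relies on a hepatic exclusion that criterion 11 does not contain; the 8.6.1 restart is no step-down on the East Asian regimen; and 8.9.3 contradicts itself on valganciclovir

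*Protocol*

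**What the plan says.** **(a) Liver.** Protocol 8.1.1 reads: "Eltrombopag will not be used in patients with hepatic impairment, which are excluded from this study (see exclusion criteria". Footnote 6 to that sentence takes impairment to be mild, moderate or severe, Child-Pugh 5 or more. It then allows use "unless the expected benefit outweighs the identified risk of portal venous thrombosis", and adds for ITP patients that "the starting dose must be 25 mg once daily". Criterion 11 in 6.2 excludes "Patients with end-stage hepatic, renal or cardiac failure, or any other life-threatening concurrent disease". The synopsis version excludes "Patients with hepatic, renal or cardiac failure, or any other life-threatening concurrent disease". Both lists add that hepatitis-associated aplastic anemia, HBV and HCV do not in themselves exclude a patient; for HBV and HCV the condition is no hepatic failure, with a reference to criterion 11.

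**(b) East Asian dose.** The standard dose is 150 mg daily. For patients of East Asian heritage 8.1.1 recommends half of that, as 50 mg and 100 mg on alternate days; footnote 4 explains this by exposure about 70% (ITP patients) to 80% (healthy subjects) higher. Section 8.6.1 stops eltrombopag above 400,000 platelets/µL. It restarts below 150,000/µL at a half-dose, which it spells out as alternating 50 mg and 100 mg, with possible escalation to 150 mg daily while the count stays below 150,000/µL. It has no variant for patients already on the reduced regimen.

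**(c) Antiviral cover.** The first sentence of 8.9.3 gives all patients daily oral valganciclovir. The second says that prophylaxis against CMV is not routine. The third allows valganciclovir, among other agents, as pre-emptive treatment guided by CMV monitoring.

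**The concern.** Eligibility and dosing rules have to be settled in the protocol itself.

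In (a), the sentence meant to keep patients with liver impairment away from eltrombopag points to an exclusion that is not in the list. The protocol's own data explain why the exclusion was wanted. Section 8.3.1 reports that, against healthy volunteers, "patients with mild hepatic impairment had approximately 87 % to 110 % higher plasma eltrombopag" AUC and "patients with moderate hepatic impairment had approximately 141 % to 240 % higher plasma eltrombopag" AUC. Of a two-week course, it also warns: "The risk of TEEs has been found to be increased in patients with chronic liver disease (CLD) treated with 75 mg eltrombopag once daily". At stake is a patient who is properly randomised to the experimental arm and then may not be given the experimental drug, or who is given it under a footnote exception that the main text rules out.

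In (b), a patient whose platelets overshot on the reduced regimen goes back on the dose that preceded the overshoot. In (c), one site may give valganciclovir to every patient and another only on viremia, and both could cite 8.9.3.

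**Working it through.** **(a) Texts side by side.**

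1. Group that may not receive the drug (8.1.1 with footnote 6): Child-Pugh 5 or more, whether mild, moderate or severe.
2. Group excluded from the trial: end-stage hepatic failure (6.2), or hepatic failure (synopsis). The two versions differ from each other, and neither reaches mild or moderate impairment.
3. Other criteria: none mentions Child-Pugh, ALT, AST or bilirubin. The clause on other life-threatening disease does not cover mild or moderate impairment.
4. Difference between 1 and 2: patients with impairment short of failure. They pass criterion 11 and fall under the 8.1.1 ban.
5. Timing: randomisation is on the day hATG starts or the day before (7.1), and eltrombopag starts on day 14 (8.1.1). Baseline liver screening (7.2.4.1) may show the impairment earlier, but no criterion acts on it. The ban therefore takes effect only at dosing, after randomisation.
6. Within 8.1.1, the main text says the drug will not be used, while footnote 6 allows it on a benefit-risk judgement. The only dose given for impairment, 25 mg, is for ITP. Section 8.3.1 asks only for caution in hepatic disease.

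**(b) Dose arithmetic.** Inputs: standard 150 mg/day; reduced regimen 50/100 mg alternating (8.1.1); restart 50/100 mg alternating, ceiling 150 mg (8.6.1); exposure 70-80% higher at equal dose (footnote 4).

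- Mean of 50/100 mg alternating: (50 + 100)/2 = 75 mg/day. Against 150 mg this is 1 - 75/150 = 50%, which reproduces the 50% reduction stated in 8.1.1.
- Step-down at restart, standard patient: 1 - 75/150 = 50%.
- Step-down at restart, patient on the reduced regimen: 1 - 75/75 = 0%.
- Escalation ceiling relative to the reduced regimen: 150/75 = 2 times.
- Exposure of an East Asian patient relative to a non-East-Asian patient on 150 mg: at 75 mg, 0.5 x 1.70 = 0.85 to 0.5 x 1.80 = 0.90, assuming dose-proportional exposure; at 150 mg, 1.70 to 1.80.

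Because 8.6.1 writes the half-dose out in milligrams, it cannot be read as half of the patient's own dose.

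**(c) Texts side by side.** The third sentence of 8.9.3 treats valganciclovir as an anti-CMV drug. Giving it daily to everyone, as the first sentence says, is then routine anti-CMV prophylaxis, which the second sentence rules out. The conflict follows from the section alone.

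**The case against.** Much can be said in the protocol's defence.

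**(a)** The no-use sentence in 8.1.1 is an operative rule, and a faulty cross-reference does not cancel it. Footnote 6 supplies a cut-off. Section 8.3.1 requires ALT, AST and bilirubin before eltrombopag starts, and Appendix 2 schedules biochemistry at day 0-1 and weekly from week 1, so liver tests are repeated before day 14. This stands. A reader might infer that impaired patients will be dosed with no rule in place; the documents do not support that, because the main-text rule is no dose. What remains is that such patients are eligible and randomised, and that the footnote undercuts the ban.

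A reader might also set the chronic liver disease finding (75 mg for two weeks) against this trial's 150 mg for at least 75 days and conclude that the risk rises in proportion. It does not follow: those patients were being prepared for invasive procedures, and nothing in the protocol supports scaling risk by dose or duration across the two settings.

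**(b)** The case is narrow. The reduction is recommended rather than required, restart waits for a count below 150,000/µL, and escalation is optional. Section 8.3.1 asks in general terms to consider a lower dose, and 8.1.1 leaves interruptions to the investigator. A lower step is thus not forbidden, but 8.6.1 provides none. A reader might go further and infer that 8.1.1.3 and 8.11.1, which name 150 mg/day, override the East Asian reduction. Both speak of the same dose and can be read back to 8.1.1, so a clarification is enough there.

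**(c)** The text applies equally to both arms, and neither patient harm nor an effect on an endpoint can be shown from it. That stands; it is a minor correction.

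**Conclusion.** All three inconsistencies are in the current text, and they carry different weight.

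- **(a) is the main point.** Patients with hepatic impairment short of failure are eligible under criterion 11 but barred from the drug by 8.1.1, and footnote 6's exception conflicts with that bar. Existing safeguards limit the risk without closing the gap.
- **(b) is certain but narrow.** The restart step-down is 0% on the reduced regimen against 50% for others, with a ceiling at twice that regimen. The exposure range of 0.85-0.90 assumes dose proportionality, and the 70-80% figures come from healthy and ITP subjects, not from aplastic anemia.
- **(c) is a wording error** to put right at the same time.

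The protocol gives no number of affected patients for any of these, and none is assumed. A reader might infer a loss of power or a bias in the 3-month response comparison; nothing here shows either, and no effect on sample size, power or the primary analysis is claimed. The case for change is patient safety and consistent conduct across sites.

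**What to change.** **(a)** Word criterion 11 identically in 6.2 and the synopsis so that it excludes hepatic impairment (Child-Pugh 5 or more), as 8.1.1 already states. Align the HBV/HCV sentence that refers to it, and say that footnote 6's benefit-risk exception does not apply in this trial. The cost is the loss of some patients now eligible; the protocol does not let their number be estimated.

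**(b)** In 8.6.1, state that patients on the reduced regimen restart below 50/100 mg alternating and escalate no further than that regimen. One possibility with the 50 mg tablets is 50 mg daily, a cut of 1 - 50/75 = 33%. This is an example only, and the coordinating investigators should confirm the step. As a clarification, add to 8.1.1.3 and 8.11.1 that the 8.1.1 reduction applies.

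**(c)** In 8.9.3, correct either the drug in the first sentence or the rule in the second.

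All of this is amendment text with the approvals set out in 14.6, plus a note to sites. Sample size and analysis are unchanged.
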